### **3 Study Subjects**

#### **3.1 Subject Accountability**

The number of subjects who were randomized, split by stratification factor (age of symptom onset: <6 and  $\geq$ 6 months), who were dosed, who completed Part 1 but not in Part 2, who completed Part 2, who discontinued treatment along with the reasons withdrawing from the study, will be presented.

Listings of those subjects who withdrew from the study and the reasons for discontinuation/withdrawal will be presented. Subjects who died during the study will be listed separately.

#### **3.2 Demography and Baseline Disease Characteristics**

Baseline data (demography, birth characteristics and SMN history, medical history and baseline characteristics) will be summarized. Medical history was collected only at screening of Part 1.

Demography includes age at Part 1 first dose ( $\leq$ 7,  $>7\leq$ 18,  $>18$  months to 2 years,  $\geq$ 2 to  $<$  3 years,  $\geq$ 3 to  $<$ 4 years,  $\geq$ 4 to 5 years, and  $>5$  years) and age at Part 2 first dose (similar categories), sex, ethnicity, and race. SMA history will include age at SMA onset (months), age at SMA diagnosis (months), and disease duration.

Baseline disease characteristics will include HINE motor milestones and growth parameters – these assessments are further described in [Section 4](#).

Baseline will generally be defined as the closest measurement before the first dose/sham procedure. For Part 2, the baseline could be the predose assessment of Day 1, or the last assessment in Part 1, depending on the actual schedule of events in Part 2 see section 1.4.

Demographic and baseline disease characteristics will be presented for the Safety set as well as both repeated by age of SMA onset (< 6 months, >= 6 months).

### **3.3 Extent of Exposure**

The number of doses and or/ sham procedures will be summarized using frequency distributions. The amount of Nusinersen received will be summarized using summary statistics.

Overall time on study will be defined as the total number of days a subject is known to be followed on study and will be calculated as follows:

Overall time on study = (Last date on study) – (Date of first dose or first sham procedure) + 1.

The last date on study is defined as the date of the latest visit or evaluation or telephone contact, or time of death from all available data for a given subject.

Given the long half-life of Nusinersen, subjects are considered to be exposed to study drug from the time the first dose was administered to the last day of follow-up. Essentially, exposure is equivalent to time on study.

The dosing and time on study will be summarized only for Part 2 and integrated data.

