Summary statistics will be presented throughout. For continuous endpoints, summary statistics will generally include number of subjects with data, mean, standard deviation, median, minimum and maximum. The mean changes from baseline will be estimated with 95% confidence intervals. For categorical endpoints, summary statistics will generally include: number of subjects dosed, number of subjects with data, and the percentage of those with data in each category. Frequency distributions will be presented as appropriate.

The statistical software, SAS® version 9.4 or above, will be used for all summaries and statistical analyses.

For Part 2, a limited number of summaries will be produced. The approach will be to preserve the Part 1 study groupings as follows for Safety and Efficacy population:

- Previous control.
- Previous ISIS 396443.
- Total (previous control and previous ISIS 396443).

For the integrated analyses, the Safety displays will be grouped as follows:

- Previous control, Part 1, from their first sham procedure in Part 1.
- Previous control, Part 2, from their first ISIS 396443 dose in Part 2.
- Previous ISIS 396443, Part 1 and 2, from their first ISIS 396443 dose in Part 1.
- Total (Previous control Part 2 and previous ISIS 396443 Part 1 and 2)

For the integrated analyses, the Efficacy displays will be grouped as follows:

- Previous control, Part 1, from their first sham procedure in Part 1.
- Previous control, Part 2, from their first ISIS 396443 dose in Part 2.
- Previous control, Part 1 and 2, from their first sham procedure in Part 1.
- Previous ISIS 396443, Part 1 and 2, from their first ISIS 396443 dose in Part 1.

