#### 4.2.2 Time to Death or Permanent Ventilation

Permanent ventilation is defined as tracheostomy or  $\geq 16$  hours of ventilatory support per day continuously for  $> 21$  days in the absence of an acute reversible event. This endpoint was not pre-specified in the protocol.

Time to permanent ventilation and acute reversible events will be determined by medical review. For all time-to-event endpoints (e.g., time to death or permanent ventilation), the date of first dose/sham administration will be used as the reference time point. If the date of first dose/sham procedure is incomplete, the date of randomization will be used. Only events that were adjudicated will be included in the analysis. Subjects who do not meet the endpoint definition will be censored at the last occasion the subject was seen (either in-person visit or by telephone contact), irrespective of whether the subject has completed a full course of treatment and whether the subject has completed the study or withdrawn prematurely. However, in the event that a subject has begun a ventilation diary, the latest entry in the diary will be used as the date of censoring. Of note, once a ventilation diary has been started, the diary will then need to be completed every day until the end of the study.

The median times to death or permanent ventilation and associated 95% confidence limits will be estimated using the Kaplan-Meier method. The proportion of subjects who meet such an event will be estimated from the Kaplan-Meier curve.

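### SAP 4.2.2 does not censor the sham curve at the first nusinersen dose, and SAP 3.3 equates exposure with a time on study that starts at the first sham procedure

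*SAP*

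**What the plan says.** SAP 1.2 has every sham child who continues start nusinersen at the beginning of Part 2. SAP Section 2 reflects this in the integrated displays. One column is "Previous control, Part 1, from their first sham procedure in Part 1" and the next is "Previous control, Part 2, from their first ISIS 396443 dose in Part 2". The integrated safety total is built from the second of these plus the previous-nusinersen children: "Total (Previous control Part 2 and previous ISIS 396443 Part 1 and 2". The efficacy displays also have a control column that deliberately joins both parts. The Part 2-only tables use the groups previous control, previous nusinersen and total, and give no starting date for any of them.

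SAP 3.3 defines "Overall time on study = (Last date on study) – (Date of first dose or first sham procedure) + 1", where the last date is the latest contact of any kind or death. It then says that "subjects are considered to be exposed to study drug from the time the first dose was administered to the last day of follow-up", and adds "Essentially, exposure is equivalent to time on study". These summaries are planned for Part 2 and for the integrated data.

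For time to death or permanent ventilation, SAP 4.2.2 says that "the date of first dose/sham administration will be used as the reference time point", a rule that Section 2 applies to all time-to-event endpoints. On censoring, "Subjects who do not meet the endpoint definition will be censored at the last occasion the subject was seen", whether or not treatment or the study was completed. If a ventilation diary exists, its latest entry is used instead, and the diary is to be kept to the end of the study. SAP 4.2.3 (survival) gives no origin, end date or crossover rule of its own.

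**The concern.** The Section 2 label for the sham Part 1 column gives a start and no end. For a child who crosses over, the last contact and the last diary entry both normally fall in Part 2, on nusinersen. A programmer who applies 4.2.2 as written would therefore leave that child in the sham curve after the switch and would count later events there. If nusinersen lowers the event rate, the tail of the sham curve would look too favourable and the contrast with the nusinersen column would shrink.

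For exposure, 3.3 makes two statements that cannot both hold for a previous-sham child: exposure starts at the first dose of drug, and exposure is the same as a time on study that starts at the first sham. If the second statement is programmed, sham days are counted as nusinersen days. Part 2's primary objective is long-term safety, and exposure time is the base on which those results are read.

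There is also no rule for a sham child who became permanently ventilated in Part 1 and then entered Part 2. The ventilation exclusion in Protocol 8.2 applies at screening, and the Part 2 exclusion rests on the investigator's judgement of a change in clinical status. Neither settles whether such a child is at risk for the composite in the Part 2 column.

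**Working it through.** The documents give no exposure, event or power figure on this point, so there is nothing to reproduce. The check is person-day arithmetic.

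Inputs:
- Planned arms: 14 nusinersen and 7 sham (Protocol synopsis).
- Planned end of Part 1: Day 422, so S = 421 days before crossover (Protocol 7.2.3).
- Planned final follow-up in Part 2: Day 897 for previous sham, so T = 897 days; Day 835 for previous nusinersen (SAP 1.4 schedules).
- Both parts ended early and actual dates are not given, so the planned schedule serves as a reference case, followed by a range.

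One previous-sham child, planned schedule:
- Counted from the first nusinersen dose: T = 897 days.
- Literal 3.3 formula: S + T = 421 + 897 = 1,318 days. Excess: 421/897 = 46.9%.

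Integrated nusinersen total, planned schedule:
- Previous nusinersen: 14 × (421 + 835) = 14 × 1,256 = 17,584 days.
- Previous sham from the first nusinersen dose: 7 × 897 = 6,279. Total 23,863 days.
- Previous sham by the literal formula: 7 × 1,318 = 9,226. Total 26,810 days.
- Excess: 2,947/23,863 = 12.3%.
- With the Section 2 origins the excess is zero.

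Sham Part 1 curve, planned schedule:
- Cut at the first nusinersen dose, it ends by 421 days.
- With no cut it runs to 1,318 days, of which 897/1,318 = 68% are on nusinersen.

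Range, assuming S of 63 to 421 days and T of 183 to 897 days (previous-nusinersen children given the same lengths, with 835 Part 2 days when T = 897):

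| S | T | Excess per sham child, S/T | Excess in integrated total | Nusinersen share of uncut sham curve, T/(S+T) |
|---|---|---|---|---|
| 63 | 183 | 34.4% | 9.3% | 74.4% |
| 63 | 897 | 7.0% | 2.3% | 93.4% |
| 182 | 365 | 49.9% | 12.5% | 66.7% |
| 421 | 183 | 230.1% | 30.3% | 30.3% |
| 421 | 897 | 46.9% | 12.3% | 68.1% |

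An invented case shows the effect on one event. A child crosses over at month 10 and has an event three months later. Under 4.2.2 as written, the sham Part 1 curve records an event at month 10 + 3 = 13. With a cut, the child is censored at month 10 in that curve and has an event at month 3 in the Part 2 column.

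**The case against.** A reader might infer that the plan ignores the crossover altogether and credits sham time to nusinersen. The documents do not support that. Section 2 restarts the integrated control Part 2 column at the first nusinersen dose and keeps sham time out of the safety total. Protocol Section 16 likewise admits only Part 2 safety data for sham children to the pooled analysis. The SAP also writes crossover rules for adverse events (5.1), concomitant therapy (3.4), imputation of motor milestones (4.5.1) and the global impression scale (4.6). Within 3.3, the sentence that starts exposure at the first dose of drug is the definition; the sentence equating it with time on study can be read as a loose gloss. The formula itself is labelled as time followed on study, for which the first sham is a proper start.

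On the end of the sham column, footnote 4 to the Part 1 schedule in SAP 1.4 dates the end of Part 1, for children who continue, at the first Part 2 dose. The 4.2.2 rule also suits the combined control column and the previous-nusinersen column as it stands. The primary Part 1 analysis is in a separate SAP that is not available here. The composite endpoint is exploratory, is declared as absent from the protocol, and is only estimated by Kaplan-Meier.

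Most of this stands and limits the point. It does not close it. A schedule footnote is not a censoring rule, and the rule actually stated in 4.2.2 names a different date without exception. The Section 2 restart labels belong to the integrated displays, so they do not give the Part 2-only exposure tables an origin.

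**Conclusion.** The point holds in a limited form: 3.3 and 4.2.2, and by extension 4.2.3, are not tied to the Section 2 columns. The firm defect is the missing cut for the sham Part 1 curve. Followed literally, the stated rule puts 68% of that curve's follow-up on nusinersen on the planned schedule, and 30% to 93% over the assumed range. The sentence equating exposure with time on study is wrong for previous-sham children, and the Part 2-only tables have no stated origin to correct it.

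The exposure figures measure a risk of misprogramming. About 12% of the integrated total on the planned schedule, or 2.3% to 30.3% over the range, would arise only if the literal formula overrode the Section 2 labels. A reader might take the larger per-child percentages as the size of the error in the total; they apply only to the previous-sham children. All sizes rest on planned arm sizes and on planned or assumed durations. A child already permanently ventilated at crossover is a possibility that the rules leave open; no document reports one.

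**What to change.** In SAP 3.3, 4.2.2 and 4.2.3, define the crossover date of each previous-sham child as the date of the first nusinersen dose, and state origin and end for each column:

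- Previous control, Part 1: from first sham to the crossover date, or to earlier death, withdrawal or last contact. Children who are event-free at crossover are censored on that date.
- Previous control, Part 2: from the crossover date to last contact. A child already permanently ventilated before that date is listed and is not at risk for the composite.
- Previous control, Part 1 and 2: keep the current rule and label the column as mixing sham and nusinersen time.
- Nusinersen exposure, in Part 2-only and integrated tables: count from the first nusinersen dose only, with the origin stated in each table. Delete or qualify the sentence equating exposure with time on study.

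The cost is SAP wording and one derived date per child, with no new data. The sham Part 1 curve becomes shorter, as does reported exposure wherever the literal formula would have been used. No hypothesis test changes.

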### **3.4 Concomitant therapy**

A concomitant therapy is any drug or substance administered between Screening and or End of study Evaluation.

Throughout the study, Investigators or designated licensed physicians involved in the study may prescribe concomitant medications or treatments deemed necessary for treatment of AEs or to provide adequate supportive care. Subjects are prohibited from receiving other experimental agents, including gene therapy, during the study. This includes marketed agents at experimental doses that are being tested for the treatment of SMA (e.g., albuterol/ salbutamol, riluzole, carnitine, sodium phenylbutyrate, valproate, hydroxyurea). All concomitant medications will be coded using the World Health Organization drug dictionary (WHO Drug).

A concomitant procedure is any therapeutic intervention (e.g., surgery/biopsy, physical therapy) or diagnostic assessment (e.g., blood gas measurement, bacterial cultures) performed between the

time the subject is enrolled in the study and End of Part 2. These will be collected on the ancillary procedure page of the eCRF and will be coded using MedDRA.

For the purposes of analysis, a concomitant therapy (including medication or procedure) is defined as any therapy that was taken or administered on or after the first injection of Nusinersen or sham procedure. For subjects receiving the sham procedure in Part 1 who subsequently roll over onto Nusinersen in Part 2, an additional definition will be applied and therapies will be considered to be concomitant medication if they were taken on or after the first dose of Nusinersen in Part 2. This definition includes therapies that were started prior to the initiation of injection of Nusinersen or sham procedure if their use continued on or after the first injection of Nusinersen. In order to define concomitant therapies with missing start or stop dates, the following additional criteria will be used:

- if both the start and stop dates of a particular therapy were missing, that therapy is considered concomitant;
- if the start date of a therapy was missing and the stop date of that therapy fell on or after the date of dosing, that therapy is considered concomitant;
- if the start date of a therapy was prior to the date of dosing and the stop date of that therapy was missing and the therapy was listed as continuing, that therapy is considered concomitant;
- if the start date of a therapy was prior to the date of dosing and the stop date of that therapy was missing and the therapy was listed as *not* continuing, that therapy is considered concomitant, or
- if the start or stop date of a therapy is partial, it will be considered concomitant where it is not possible to rule out that it was not taken concomitantly.

The number and percentage of subjects who were taking each type of concomitant medication at baseline and during the study will be presented. The number and percentage of subjects taking each type of ancillary procedure will be presented by preferred term.

### **3.5 Protocol deviations**

Protocol deviations identified during site monitoring will be captured in a protocol deviation log and categorized as major or minor deviations. These deviations will be listed. Major protocol deviations will be summarized for only Part 2 as part of this SAP.

## 4 Efficacy data (exploratory)

### 4.1 Visit Windowing

#### *Part 2 analysis*

Part 2 will terminate early and the end of study visit will occur at different time points, for this reason the end of study visit will be re-labeled and windowed as follow:

- If the actual study day falls within +/- 7 days of any of Part 2 Day xx visit, the end of study visit will be re-labelled as the corresponding scheduled visit.
- Otherwise, the end of study visit will be re-labelled as an unscheduled visit.

#### *Integrated analysis*

The HINE motor milestones, growth parameters and CGI, laboratory data, CSF and Plasma concentrations integrated analyses will be windowed as follows:

Study days  $\leq 1$  will be labelled Baseline

- Study days  $> 1$  to  $\leq 22$  will be labelled Day 15
- Study days  $> 22$  to  $\leq 47$  will be labelled Day 29
- Study days  $> 47$  to  $\leq 123$  will be labelled Day 64
- Study days  $> 123$  to  $\leq 242$  will be labelled Day 183
- Study days  $> 242$  to  $\leq 362$  will be labelled Day 302
- Study days  $> 362$  to  $\leq 482$  will be labelled Day 422
- Study days  $> 482$  to  $\leq 600$  will be labelled Day 540
- Study days  $> 600$  to  $\leq 719$  will be labelled Day 659
- Study days  $> 719$  to  $\leq 838$  will be labelled Day 778
- Study days  $> 838$  to  $\leq 958$  will be labelled Day 898
- Study days  $> 958$  to  $\leq 1078$  will be labelled Day 1018
- Study days  $> 1078$  to  $\leq 1198$  will be labelled Day 1138

If multiple results are allocated into the same window then the closest non-missing result to the target date will be chosen.

In order to account for the denominator across the analysis visits, an Efficacy set for each windowed analysis visit (Day X) will be defined as: a subset of subjects in the Safety set who have the opportunity to be assessed at the Day X visit, where the lower bound for the windowed analysis visit are denoted: L= lower. Specifically, it will include all subjects with a time difference of at

least L days between the date of first dose and the end of Part 2. A subject who has died or withdrawn will be included provided that there is a difference of at least L days between the date of first dose and the end of Part 2. In a situation where the subject was known to have withdrawn from the study at a date within the window due to rolling over to commercial drug then they will be excluded from the corresponding Efficacy set and subsequent analysis visit Efficacy sets.

An evaluable set will be defined for each analysis visit as the subset of subjects in the Efficacy set at the analysis visit who meet the following criteria:

- Value assigned from the windowing
- Subject who died or discontinued from the study – no imputation of efficacy data will be performed for such subjects and they will be considered non-responders.
- No value assigned from windowing, but ongoing in study with a subsequent assessment assigned to a later analysis visit. In this situation, a value will be imputed as the value from the analysis visit prior to the missing visit.

A couple of considerations as part of this final criterion are as follows:

- In a situation where a subject does not have a windowed value at analysis visit X and is known to discontinue at the next visit, X+1, without an efficacy assessment, the subject would not be included within the denominator for the responder analysis at visit X, but they would be included as a non-responder at visit X+1.
- In a situation where a subject does not have a windowed value at analysis visit X and is known to discontinue at the next visit, X+1, with an efficacy assessment prior to the discontinuation, the subject would be included within the denominator for the responder analysis at visit X and the last observed value will be utilized, and then they would be included as a non-responder at visit X+1.

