- ⁹ At the evaluations scheduled for injection of study treatment or sham procedure, subjects will be assessed for the following growth parameters: body length, head circumference, chest circumference, and arm circumference.
- ¹⁰ Neurological examinations include assessment of mental status, level of consciousness, sensory function, motor function, cranial nerve function, and reflexes.
- ¹¹ Neurological examinations will occur between 4 to 6 hours after the injection of study treatment or sham procedure.
- ¹² Blood chemistry, hematology, and urinalysis panels.
- ¹³ Samples for safety laboratory tests will be collected before the injection of study treatment or sham procedure on Days 64 and 183 only.
- ¹⁴ End of Part 1 safety laboratory tests may be performed locally in addition to centrally to accommodate the Part 2 Day 1 dosing.
- ¹⁵ Refer to [Table 5](#) for CSF PK sample schedule. The CSF samples will be analyzed for Nusinersen concentrations. The remaining CSF sample will be stored for optional future biomarker analyses.
- ¹⁶ Blood samples for PK assessment will be collected 4 hours (± 1 hour) after the injection of study treatment or sham procedure only on Day 1. Refer to [Table 5](#) for the plasma PK sample schedule.
- ¹⁷ Blood samples for PK assessment will be collected before the injection of study treatment or sham procedure on Days 64 and 183 only. Refer to [Table 5](#) for the plasma PK sample schedule.
- ¹⁸ Overnight stay (at least 24 hours) is required after the first injection of study treatment or sham procedure. Following all subsequent injections or sham procedures, a stay of at least 6 hours at the study site is required; overnight stays are optional on these days.
- ¹⁹ In addition to concomitant medications, ancillary procedures will be recorded.
- ²⁰ AEs and SAEs will be collected in the case report form from the time of signing of the informed consent form as described in [Section 15.3.1](#) and [Section 15.3.2](#).

CONFIDENTIAL

The information contained herein may not be used, disclosed, or published without the written consent of Biogen MA Inc.

4.2.2. Schedule of Events: Part 2

Table 3: Part 2 Schedule of Activities for Subjects Randomized to Receive Nusinersen in Part 1

Study Period	Part 2 Treatment/Follow-Up									
	Study Day	Day 1			Day 2 ¹	Days 120, 239, 358, 477, 596, 715 (± 7 days) ²			Days 121, 240, 359, 478, 597, 716 ¹	Part 2 Final Follow-Up (Day 835 [± 7 days]) ³ or Part 2 Early Termination ⁴

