-  ECG will be performed on Days 239, 477, and 715, and at the Part 2 Final Follow-up Evaluation. ECG must be performed before obtaining blood samples for safety laboratory tests.
-  Blood chemistry, hematology, urinalysis, urine total protein panels, and coagulation parameters. Urine total protein and coagulation parameters will be assessed by local laboratories.
-  Samples for safety laboratory tests will be collected before the injection of study treatment at each dosing visit.
-  Blood samples for immunogenicity testing will be collected before the injection of study treatment on Days 239, 477, and 715.
-  Refer to **Error! Reference source not found.** for CSF PK sample schedule. The CSF samples will be analyzed for Nusinersen concentrations. The remaining CSF sample will be stored for optional future biomarker analyses.
-  Blood samples for PK assessment will be collected 4 hours ( $\pm 1$  hour) after the injection of study treatment only on Day 1. Refer to **Error! Reference source not found.** for the plasma PK sample schedule. Plasma PK samples will be collected predose on Days 239, 477, and 715.
-  The optional assessment of sibling SMA data collection will be performed only after obtaining consent.

In addition to concomitant medications, ancillary procedures will be recorded.

AEs and SAEs will be collected in the case report form from the time of signing of the informed consent form as described in Section and Section 15.3.2 of the protocol.

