### PK Part1

Table 3 Part 1 Pharmacokinetic Sampling Schedule				
Treatment Period	Part 1 Study Day	Timepoints	Blood Collection (mL)	CSF Collection (mL)
Multiple Dose: LP Injection	Day 1	Predose	NA	0.5
		4 h ( $\pm$ 1 h) postdose	0.5	NA
	Day 15	Predose	NA	0.5
	Day 29	Predose	NA	0.5
	Day 64	Predose	0.5	0.5
	Day 183	Predose	0.5	0.5
	Day 302	Predose	NA	0.5
	End of Part 1	NA	0.5	NA

CSF = cerebrospinal fluid; h = hour; min = minutes; LP = lumbar puncture; mRNA = messenger ribonucleic acid; NA = not applicable (no collection scheduled); SMA = spinal muscular atrophy.

 Details on sampling, preparation, and shipment are included in the Study Laboratory Manual.

 Upon consent, the collected CSF samples from the study subjects will be stored for future investigation of possible biomarkers of SMA disease (e.g., CSF mRNA, CSF protein, CSF microRNA panel), for profiling of study drug binding proteins, bioanalytical method validation purposes, stability assessments, metabolite assessments, and immunogenicity assessments (including assay development and validation purposes), or for assessing other actions of Nusinersen with plasma and CSF constituents.

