### PK Part2

Table 4 Part 2 Pharmacokinetic Sampling Schedule for Subjects Randomized to Receive Nusinersen in Part 1				
Treatment Period	Part 2 Study Day	Timepoints	Blood Collection (mL)	CSF Collection (mL)
Multiple Dose: LP Injection	Day 1	Predose	NA	0.5
		4 h ( $\pm$ 1 h) postdose	0.5	NA

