## **2 Statistical Methods: General Considerations**

In this SAP, the terms “control” and “previous control” refer to the set of subjects who were randomized to undergo the sham procedure during the Part 1.

In order to distinguish nominal visit names from duration defined in days, visit names will be referred to as “Day 15”, “Day 29”, etc., and “15 days” or “29 days” etc. will be used to define time intervals.

Due to emergent data from the Nusinersen clinical development program, the subjects in Part 1 ended the study early as follows: subjects randomized to sham terminated Part 1 first irrespective of Part 1 planned dosing days and subjects randomized to Nusinersen transitioned to Part 2 accordingly to their specific dose schedule. Part 2 was also terminated early to allow subjects to

enter the ISIS 396443-CS11 study. For these reasons, the actual study day associated with visits Part 1 and Part 2 will vary widely amongst subjects. Therefore, a windowing schema will be implemented for by visit analyses (see [section 4.1](#))

The safety population will include all subjects who are randomized and receive at least 1 dose of study treatment or sham procedure. Subjects randomized to receive sham procedure but incorrectly treated with Nusinersen will be counted in the ISIS 396443 group from the first dose of Nusinersen received.

The Efficacy set at each visit will be defined as the subset of subjects in the Safety set who has had the opportunity to be assessed at that visit (actual visit for Part 2 or windowed visit for integrated analysis see [section 4.1](#))

The PK population will include all subjects who are randomized and have at least 1 evaluable post dose or post sham-procedure PK sample.

The immunogenicity population will include all subjects who are randomized and have at least 1 evaluable post dose or post sham-procedure immunogenicity data.

For all time-to-event endpoints, (e.g., time to death or permanent ventilation), the date of first dose/sham administration will be used as the reference time point. If the date of first dose/sham procedure is incomplete, the date of randomization will be used.

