## **6 Pharmacokinetic data**

CSF and plasma samples will be collected at protocol designated times for Nusinersen or sham procedure pharmacokinetic assessments in the Pharmacokinetic Population. The Pharmacokinetic Population includes all subjects who are dosed and for which there is at least one evaluable post-dose procedure pharmacokinetic sample.

The PK analysis will be on integrated data and the same windowing approach used for the efficacy analysis will be used.

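### Three SAP rules for nusinersen concentrations give wrong or undefined entries: 4-hour post-dose plasma labelled as baseline, kit fluid reported as sham CSF, and zeros entered into geometric statistics

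*SAP*

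**What the plan says.** **Windowing.** SAP section 4.1 lists the concentration data among the items to be windowed ("laboratory data, CSF and Plasma concentrations integrated analyses will be windowed as follows"), and section 6 repeats it for PK: "The PK analysis will be on integrated data and the same windowing approach used for the efficacy analysis will be used". Study days up to and including 1 are labelled baseline, with no condition on whether the sample came before or after dosing. Where two samples compete, "If multiple results are allocated into the same window then the closest non-missing result to the target date will be chosen". No rule covers equal distances.

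**Plasma sampling.** In Part 1, blood for PK is taken 4 hours (±1 hour) "after the injection of study treatment or sham procedure only on Day 1" (protocol Table 2, footnote 16). Protocol Table 5 and SAP Table 3 show no pre-dose blood on Day 1. For prior-nusinersen subjects in Part 2 the sample is again 4 hours "after the injection of study treatment only on Day 1", with no pre-dose blood that day (SAP Table 4). A plasma sample is also scheduled at End of Part 1.

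**Sham CSF.** Protocol section 11.1.2 describes the sham as a skin prick without lumbar puncture, and says artificial CSF from the kit stands in for the subject's CSF sample. SAP section 6.1 nevertheless tabulates sham-procedure CSF concentrations by windowed visit and plots them over time.

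**BLQ values.** SAP sections 6.1 and 6.2 set BLQ results to zero for a list of statistics that includes the geometric mean and geometric %CV. A mean that is itself BLQ is shown as BLQ, with SD and %CV not applicable. Nothing is said about the geometric statistics.

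**The concern.** Nusinersen concentration in plasma and CSF is the secondary endpoint of both Parts, and the windowed tables are its planned numerical summary. A reader of the plasma table would take the baseline row for drug-naive values when it holds values drawn close to the expected peak: protocol section 5.3.1 reports a plasma peak at 4 hours in monkeys. Rollover rows could mix post-dose and end-of-interval values according to visit dates. The sham CSF rows would describe the contents of a vial. Geometric means would print as zero in any row with a single BLQ value.

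**Working it through.** The plan gives no figure to reproduce here. The check passes each scheduled sample through the stated rules.

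**(a) Plasma windows.** Inputs: the windows in SAP section 4.1 and the sampling days in SAP Tables 3 and 4.

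- The Part 1 Day 1 4-hour sample has study day 1. Since 1 ≤ 1, it is labelled baseline. No other Day 1 plasma sample exists, so the row holds post-dose values for every nusinersen subject with a Day 1 sample: 14 of 14 planned.
- At rollover, distance from target decides. Three date examples, in integrated study days:

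| End of Part 1 sample | Part 2 Day 1 4-hour sample | Window (target) | Distances | Kept |
|---|---|---|---|---|
| 295 | 302 | >242 to 362 (302) | 7 and 0 | 4-hour sample |
| 422 | 429 | >362 to 482 (422) | 0 and 7 | End of Part 1 sample |
| 302 | 302 | >242 to 362 (302) | 0 and 0 | undecided |

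The third case can occur because protocol section 7.2.2 lets a subject move to Part 2 immediately after the End of Part 1 assessments. The first is plausible because SAP section 2 says that "subjects randomized to Nusinersen transitioned to Part 2 accordingly to their specific dose schedule", which can put Part 2 Day 1 near a target.

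- CSF timing is not affected. Every scheduled CSF sample is pre-dose, so Day 1 CSF is correctly baseline.

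**(b) Kit fluid.** Inputs: 6 scheduled Part 1 CSF collections per subject (SAP Table 3), 7 planned sham subjects, 21 planned in all. Sham samples: 6 × 7 = 42. All Part 1 samples: 6 × 21 = 126. This is a ceiling, because Part 1 stopped early.

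**(c) Zeros.** The geometric mean is exp(mean of ln x), and ln 0 is minus infinity, so one zero gives a geometric mean of 0. The geometric %CV, 100 × √(exp(SD(ln x)²) − 1), is undefined. Example with one BLQ value and thirteen values of 5: geometric mean 0; arithmetic mean 65/14 = 4.64; geometric mean of the quantifiable values 5.

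The SAP gives no BLQ rate. If each value were independently BLQ with probability p (an assumption), a 14-subject row would contain at least one with probability 1 − (1 − p)^14: 13% at p = 1%, 51% at 5%, 77% at 10%.

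**The case against.** The best defence is that little depends on these tables. No PK test or PK change from baseline is planned. Listings carry nominal and actual sampling times, individual profiles use actual time, and mean profiles use scheduled time, so the nusinersen data stay recoverable. The sham values are labelled as sham, and nothing says they are pooled with nusinersen values. Whether the laboratory assays the kit fluid is not stated. The zeros matter only in rows that contain a BLQ value, and the arithmetic mean, median, minimum and maximum survive. All of that stands, and it limits the severity.

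It does not remove the defects. The discretionary exclusion in sections 6.1 and 6.2 covers large timing or dose deviations, and a 4-hour sample taken on time is neither. Section 6 limits the PK population to dosed subjects, but section 2 admits post-sham samples, section 6.1 names them, and sham subjects who enter Part 2 are dosed.

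Some stronger readings are tempting and not supported:

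- *That the 4-hour sample will usually displace the End of Part 1 sample.* The documents give no distribution of dates. Take an assumed grid of 15 offsets (±7 days from target) × 31 gaps (0 to 30 days) = 465 equally weighted date pairs. The 4-hour sample is kept in 394 with Part 2 Day 1 anchored at the target, but in only 49 with End of Part 1 anchored at Day 422. The answer reverses with the anchor.
- *That same-day ties are the norm,* because footnote 4 of the Part 1 schedule dates End of Part 1 as the first Part 2 dose for rollover subjects. That footnote sets the boundary between Parts and does not re-date the End of Part 1 sample. Footnote 7 of the Part 2 schedules foresees dosing more than 24 hours, or more than 30 days, after the End of Part 1 visit.
- *That CSF pNf-H results are contaminated.* SAP section 4.8 does not exclude kit fluid, so this is possible, but it is not stated.
- *That former sham subjects' plasma baseline is displaced in Part 2.* That depends on a PK display grouping the SAP does not give.

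**Conclusion.** All three rules give wrong or undefined output if followed as written. The baseline mislabel is certain on the text and affects the plasma row for all 14 planned nusinersen subjects; in the sham arm it does no harm, since no drug was given. The rollover selection is a gap in the rule, and the documents allow no frequency to be attached to it. Sham CSF is at most 42 of 126 planned Part 1 samples. The BLQ problem arises in any row with at least one BLQ value; how many rows that is cannot be known from the documents, and the probabilities above rest on assumed independent rates. The effect is confined to descriptive windowed tables and the sham CSF plots. Severity is minor to moderate.

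**What to change.** - **Plasma.** Report the 4-hour samples in their own nominal-time rows (Part 1 Day 1, 4 hours; Part 2 Day 1, 4 hours). Apply the windows only to pre-dose and follow-up samples, and build no plasma baseline row from post-dose samples. This also removes the rollover conflict, because no pre-dose plasma is scheduled on Part 2 Day 1. State a tie rule for any other case.
- **CSF.** Exclude sham-arm Part 1 kit fluid from the CSF PK summaries and plots, and from any CSF pNf-H summary should it be assayed. Use Part 2 Day 1 pre-dose CSF as those subjects' CSF baseline.
- **BLQ.** Keep zero for the arithmetic statistics. Compute geometric statistics on quantifiable values only, and show the number BLQ in each row.

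The cost is SAP wording and minor programming. Former sham subjects would have no Part 1 CSF rows. Geometric means on quantifiable values run high when BLQ is common. For lognormal data the factor is exp(s·φ(z)/(1 − p)), with s² = ln(1 + CV²), φ the standard normal density and z the p-quantile. At assumed CVs of 50% and 100% this gives 1.10 and 1.18 at 10% BLQ, and 1.18 and 1.34 at 20%. The BLQ count must therefore stand beside the figure.
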